## 3) Other expected adverse events

The following adverse events have been reported in patients who received this product in clinical trials. The effect of this product on the incidence of these adverse events is unclear. These adverse events include cardiogenic shock, heart failure, cardiac rupture and electromechanical separation, ventricular fibrillation, and cardiac rupture (3.23%); increase in aminotransferase, myocardial enzyme, blood lipid and blood glucose, as well as nausea, vomiting, fever and cough, all mild. The majority of these adverse events are determined not to be related to the test drug, but to underlying and/or comorbidities, as well as concomitant drugs.

The relationship between the above events and TNK-TPA is not clear, and most of them are potential combined diseases. If the above phenomena occur, appropriate treatment should be taken according to the situation.

## 4) Other adverse reactions

Other adverse reactions should be analyzed by the investigator according to the specific situation, and given symptomatic treatment according to the corresponding treatment guidelines or clinical routine procedures.

## 10. Data management

## 10.1 Source data/source files

Source data refers to all information recorded in the original records or copies (certified copies) of the clinical trial, including clinical findings, observations, and other relevant activity records necessary for reconstruction and evaluation of the clinical trial.

Source documents refer to the original medical records, medical documents and data generated during the clinical trial. Source file contains the source data, such as the hospital medical records, medical images, laboratory records, clinical trial related memorandum, clinical trial subjects the diary or assessment form, hair medicine, instruments and automatic recording of data and save the prescription pharmacy, laboratory and the department of medical and related documents and records, including duplicated or copied certified copy thereof. Source files can be paper and/or electronic.

The investigator and the medical institution to which he/she works permit the Sponsor to supervise or audit the clinical trial; The health administration and drug supervisory and regulatory authorities have the right to inspect clinical trials and have direct access to source data/source documents.

### 10.2 Database establishment and data entry

- (1) Selection of EDC system: In this clinical study, EDC system is used to collect eCRF data.
- (2) Database establishment: build eCRF interface according to protocol and CRF table, and set logical review limit conditions; Input the test data to carry on the trial operation of the database, and then establish the special database system for the trial.
- (3) Data entry: each user will get an independent user name and password. The designated personnel of the research center will input the original data into the eCRF through the secure network. The system will automatically check the data deviation in the eCRF, generate the corresponding prompt message, and allow the personnel of the research center to modify the input data.

The clinical research associate should confirm that all data in the eCRF is consistent with the original record. Any errors or omissions found will be notified to the staff of the Research Centre in the form of a query sheet requesting modifications to the relevant data in the eCRF. Before the database is locked, the investigators will confirm and electronically sign off to ensure the accuracy of the data recorded.

## 10.3 Data monitoring

Monitoring of eCRF data and process files:

- (1) During the study, the clinical research associate shall come to the research center to check the informed consent and screening and enrollment of the subjects.
- (2) Confirm that all eCRFs are filled correctly and consistent with the original data.
  - (3) Adverse events of each subject shall be confirmed and recorded.
  - (4) The withdrawal of the subject shall be explained in the eCRF.
- (5) Confirm that all AE's have been documented and that SAE has made a report for the record.
- (6) Verify whether the study drugs are supplied, stored, distributed and recovered in accordance with relevant regulations, and make corresponding records of the storage conditions, time and records of the remaining study drugs in accordance with relevant requirements.

ECRF data, analytical data and process documents will be stored on paper or electronically. After the database is locked, the locked data will be transferred to the Sponsor.

### 10.4 Quality assurance of research data

To ensure the accuracy, integrity and reliability of the data, the investigator needs to record all trial data and procedures, including informed consent signing, screening, medication and blood sample collection, and laboratory analysis data. If necessary, the investigator should provide the original data to the Sponsor, the relevant regulatory authorities, and the Ethics Committee.

The Sponsor will designate relevant personnel to complete the following work:

- (1) Provide appropriate instructional research documents and materials to the research center.
- (2) The Sponsor will organize a kick-off meeting to train the investigators and study coordinators before the study begins. This meeting will explain the study protocol, eCRF filling and study procedure.
  - (3) Regular follow-up research center for related quality control.
- (4) Keep in touch with the Research Centre at all times by telephone, mail and/or fax.
- (5) Check and evaluate eCRF data in a timely manner, analyze quality, or use standardized computer editing to detect errors in data collection.

In addition, the Sponsor or designated representative will visit the study center periodically to check that the subject data is consistent with the original records and may audit the study at any time.

## 10.5 Data review and locking

The data management facility reviews the data recorded in the eCRF in accordance with the standard operating procedures. For any questions in the data, the data management personnel will question the research center personnel in the form of an electronic query sheet, requesting the personnel designated by the research center to answer the questions and make some necessary modifications to the data. All data changes and related operations need to be documented. The data administrator shall write the data audit report according to the final version study protocol, data audit standard and database. The project manager will organize the Sponsor, major

investigators, statisticians and data administrators to hold a data review meeting to review the data, and the representatives of all parties will sign the review resolution. After the parties approve the database locking, the data administrator organizes the database locking work and submits the locked database to the statistician for statistical analysis.

### 11. Sample size

In this study, rt-PA active control will be used based on a statistical hypothesis test of non-inferiority, and the proportion of subjects with 90-day MRS score of 0-1 will be used as the primary efficacy endpoint.

According to a paper published in the Lancet[7] in 2014 about meta-analysis of the incidence of 90-day MRS score of 0-1 (treatment within 4.5h) regarding rt-PA versus Placebo, the RR and 95% confidence interval were 1.24 and 1.14-1.36, respectively. According to the Guidelines for the Design of Non-inferiority Drug Clinical Trials [32], the lower 95% confidence interval of the Meta analysis should be used to calculate the non-inferiority threshold given that the primary endpoint is a high priority index. Therefore, based on the lower CI limit of 1.14, together with an efficacy of 50% of the active control, the non-inferior threshold was determined as 0.937. Then assuming  $\alpha$ =0.025 using one-sided test, power 1- $\beta$ =0.85, treatment group (TNK) incidence of 63.64%, control group (rt-PA) incidence of 59.32%, RR= 1.07, the sample size was calculated to be 642 cases in each group; considering a dropout rate of 10%, the sample size was determined as 715 cases in each group and the total sample size is estimated to be 1430 cases.

#### 12. Statistical plan

## 12.1 Statistical analysis

Full analysis set (FAS), per protocol set (PPS) and safety analysis set (SAS) will be established according to the NMPA regulations for data statistical analysis. Strict quality control will be carried out in the whole process of data collection to ensure the authenticity of the evaluation data.

Full analysis set (FAS): a data set consisting of all subjects randomized to receive at least one study drug according to the basic principle of Intention To Treat.

Per protocol set (PPS): PPS includes all subjects who complete the stipulated treatment without missing primary efficacy endpoints or serious violations of the protocol. Serious protocol violation will be finally defined during data review and

may generally include (but not limited to) the following situations: subjects violating inclusion criteria or exclusion criteria, poor compliance in stipulated medication, concomitant medication that affects outcome indicators, and out of visit window.

Safety analysis set (SS): a set of all subjects participating in the trial, receiving at least one study drug, and having at least one safety evaluation.

FAS and PPS are established as sensitive analysis groups; Efficacy analysis is performed on the basis of FAS and PPS. Safety endpoints will be performed on the safety set and safety missing data will not be filled. All baseline demographic data analyses will be performed on the basis of the FAS; illogic data needs to be investigated by the data management facility, investigators or Sponsor together to identify possible reasons, and restrained by the parties in a data review meeting after full discussion: illogic data, if sufficient reasons have been found to indicate its incorrectness, should be removed, or otherwise, should be remained and subjected to analysis and the results obtained without such removed data should be treated as sensitivity analysis; If there is data collected in the study that is not in accordance with the program requirements such as planned external visits, it will be presented in a list, and descriptive or comparative analysis will be decided at the data review meeting depending on the specific situation of the data.

## 12.2 General principles

All statistical analysis will be conducted by SAS9.4 or higher version statistical software. The content of statistical analysis in the protocol is the general principle of statistical analysis method, and the specific statistical analysis process will be carried out according to the pre-formulated statistical analysis protocol.

Statistical description: quantitative indicators describe mean, standard deviation, minimum, maximum, median, quartile, etc. Qualitative indicators describe the number and percentage of cases in each category or grade.

Statistical inference: the two-sample t-test or non-parametric test is used for the comparison of quantitative indicators between groups depending on the data situation, the non-parametric test is used for the comparison of grade indicators, and the Chi-square or Fisher exact probability method is used for qualitative indicators. Evaluation of efficacy endpoints will be considered for inclusion in baseline or center effect analyses depending on the specific situation.

Statistical hypothesis: Comparison of the primary efficacy endpoint between groups is conducted by a one-sided test, with a significance level of one-sided  $\alpha$ =0.025; null hypothesis H0: RR  $\leq \Delta$  and alternative hypothesis H1: RR  $> \Delta$ ; RR is the ratio of incidence of the treatment group and the control group;  $\Delta$  is 0.937 as the non-inferior threshold; when P < 0.025 or lower limit of 95% CI of RR > 0.937 in non-inferiority tests, it indicates that the test drug is not inferior to control drug; if the primary efficacy endpoint meet non-inferiority criteria, the superiority test will be conducted and the test threshold  $\Delta$  is set to 1; when P<0.025 or lower limit of 95% CI of RR > 1 in superiority tests, it indicates that the test drug is superior to control drug. All other statistical analyses are conducted by two-sided tests, with a significance level of two-sided  $\alpha$ =0.05. When P $\leq$ 0.05, it indicates a statistically significant difference. The confidence interval is 95% on both sides. Primary-efficacy-endpoint hypothesis tests are as follows:

$$H_0$$
:  $RR_{试验组/对照组} \leq \Delta H_0$ :  $RR_{试验组/对照组} \leq \Delta$   $H_1$ :  $RR_{试验组/对照组} > \Delta$   $H_1$ :  $RR_{试验组/对照组} > \Delta$ 

#### 12.3 Analysis content

The actual number of subjects enrolled in each group, completed and dropped out from the study, removed, deviated from or violated the protocol, demographic and other baseline characteristics, compliance, efficacy analysis, and safety analysis. Statistical analysis includes (1) the case number of completed and that of dropped out in each research center, etc.; (2) The demographic and baseline characteristics of each group at the time of enrollment, necessary for comparability analysis between the treatment group and the control group; 3) Efficacy evaluation and safety evaluation, as described below.

### 12.4 Efficacy evaluation

Primary efficacy endpoints

Description method: Patients with 90-day MRS score of 0-1 among all enrolled patients in the corresponding data set is statistically described in the form of number and percentage respectively.

Analysis methods: in this protocol, the primary endpoint is the proportion of subjects with 90-day mRS score of 0-1; for such endpoint, CMH test with controlled

center effect will be applied to statistically compare the treatment group and control group, and the 95% confidence interval of efficacy, and corresponding RR or RD and corresponding 95% confidence interval will be calculated; Logistic regression model analysis will also be considered to report the 95% confidence intervals of OR for TNK-TPA versus rt-PA. Adjustment for covariates with inter-group differences or center-group interactions will be made as appropriate.

Analysis of secondary efficacy endpoints

#### Include:

- 1) The proportion of subjects with an mRS score of 0-2 at  $90\pm7$  days
- 2) MRS level distribution at 90±7 days (Shift Analysis /Ordinal Distribution)
- 3) The proportion of subjects whose NIHSS score is 0-1 or is improved compared to the baseline with  $\Delta$  NIHSS  $\geq$  4 at 24±2h, 7±1d or before discharge (whichever comes first)
- 4) Health-related quality of life (EQ-5d) at 90±7 day
- 5) The proportion of subjects with a Bathel score  $\geq$  95 points at 90±7 days

The analysis of secondary endpoints refers to the general principles of statistical analysis. For secondary efficacy outcomes, common odds ratio with its 95% confidence interval was calculated using ordinal logistic regression for the outcome of ordinal 90-day mRS score, and odds ratios with their 95% confidence intervals were calculated using binary logistic regression for other secondary efficacy outcomes.

Subgroup analysis: In this study, bridging therapy is performed within 24h of thrombolysis. Because bridging therapy may be a potential outcome influencing factor, bridging therapy is predesigned as a covariate in the subgroup analysis, and the RR values and 95% confidence intervals of the incidence of the trial and control groups in each subgroup are calculated respectively.

### 12.5 Safety evaluation

The number and incidence of safety endpoints in each group are statistically described. The number of cases and events, and incidence of adverse events and adverse reactions in each group are statistically described, and the specific list of adverse events is described. Chi-square or Fisher tests are used to compare whether

there are differences between groups in safety endpoints. Laboratory data and other safety data will be descriptive statistics, and the data before and after treatment will be compared by paired t test, mainly to analyze and list the specific situation of normal cases before treatment but abnormal cases after treatment or abnormal cases before treatment but aggravated cases after treatment.

Primary safety evaluation endpoints:

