# Statistical analysis

#### Safety endpoints:

Chi-square test or Fisher's exact probability method are used for qualitative classification, and 95% confidence intervals for incidence differences between groups are calculated. Qualitative grade data are analyzed by Wilcoxon rank sum test, and quantitative indicators are analyzed by two-sample t-test or rank sum test as appropriate, and 95% confidence intervals for score differences between groups are calculated.

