#### Secondary study objectives:

- 1. To compare the difference in efficacy between rhTNK-tPA (0.25 mg/kg) and standard rT-PA (0.9mg/kg) in the treatment of hyperacute ischemic stroke (within 4.5 h of symptom onset) subjects:
- (1) The proportion of subjects with an mRS score of 0-2 at 90±7 days
- (2) MRS level distribution at 90±7 days (Shift Analysis /Ordinal Distribution)
- (3) The proportion of subjects whose NIHSS score is 0-1 or is improved compared to the baseline with  $\Delta$ NIHSS  $\geq$  4 at 24±2h, 7±1d or before discharge (whichever comes first)
- (4) Health-related quality of life (EQ-5d) at 90±7 day
- (5) The proportion of subjects with a Bathel score  $\geq$  95 points at 90±7 days
- 2. To compare the difference in safety between rhTNK-tPA (0.25 mg/kg) and standard rT-PA (0.9mg/kg) in the treatment of subjects with hyperacute ischemic stroke (within 4.5 h of symptom onset):
  - ① The incidence of symptomatic intracranial hemorrhage within 36 hours (as defined by ECASSIII)
  - 2 The incidence of symptomatic intracranial hemorrhage within 90 days (as defined by ECASSIII)
  - (3) The incidence of PH2 intracranial hemorrhage within 36 hours (according to SITS standards)
  - (4) The incidence of any intracranial hemorrhage within 90 days
  - (5) The incidence of significant hemorrhage events at other sites within 90 days (as defined by GUSTO)
  - 6) 90-day overall mortality
  - 7 Incidence rates of adverse events/serious adverse events within 90 days

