## 2 Evaluation of laboratory test indicators

Include routine blood test, routine urinalysis, blood biochemistry and lipid indexes.

The number of cases is described for each kind of clinical judgment result (normal, abnormal without clinical significance, abnormal with clinical significance and not tested) of laboratory examination results before and after treatment in the form of a cross table.

The patients who are judged to be abnormal after the treatment are described in detail by nature (with clinical significance, without clinical significance, or not tested) in the form of lists.

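### Protocol 12.5 names only a before/after paired t test for laboratory data; it tests change over time, not the treatment difference, and needs reconciling with the between-group rules

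*Supplement*

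**What the plan says.** The second group of secondary objectives in protocol section 2 is comparative: "To compare the difference in safety between rhTNK-tPA (0.25 mg/kg) and standard" alteplase. It is then spelled out in seven items covering intracranial and other bleeding, death, and adverse events.

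The protocol text that bears on laboratory values is as follows.

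- **Section 12.5, opening paragraph:** laboratory and other safety data are to be summarised descriptively, and "the data before and after treatment will be compared by paired t test". The stated purpose follows at once: "mainly to analyze and list the specific situation of normal cases before treatment but abnormal cases after treatment", or cases already abnormal that got worse. The text does not say whether the paired test is run in each arm or in both arms together.
- **Section 12.5, laboratory subsection:** counts of "laboratory examination results before and after treatment in the form of a cross table", plus lists of abnormal patients. It names blood, urine, biochemistry and lipid tests. Coagulation is not among them, although sections 7.1, 7.4.1 and 7.4.3 measure it at baseline, at 24 h, and at day 7 or discharge.
- **Section 12.2, general rule:** "the two-sample t-test or non-parametric test is used for the comparison of quantitative indicators between groups depending on the data situation".
- **Protocol summary, statistical analysis of safety endpoints:** "quantitative indicators are analyzed by two-sample t-test or rank sum test as appropriate, and 95% confidence intervals for score differences between groups are calculated".

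Section 13 of the final SAP covers bleeding events, adverse events, deaths and serious adverse events. It contains no laboratory analysis.

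**The concern.** A paired t test of post-treatment against pre-treatment values asks whether the mean changed. In this trial every patient has a hyperacute stroke, receives a thrombolytic and is treated in hospital. Mean laboratory values can therefore move in both arms for reasons that have nothing to do with which drug was given. A significant result does not separate these causes, and a non-significant one does not show that the drugs are alike.

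The test also misses its own stated purpose. It concerns a mean, whereas the aim is to find individual patients who became abnormal or worsened. A shift table or a listing does that; a test of mean change does not. This fault does not depend on any assumption about drift.

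Two things are at stake. If the test is run by arm, significance in one arm and not the other invites a claim of a difference that was never tested. And a real difference between the drugs in a measured value, such as fibrinogen or haemoglobin, might go unestimated although the data are collected. How exposed the plan is depends on whether the general between-group rules apply to laboratory values, and the documents leave that open.

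**Working it through.** **Sample size for the illustration.** The plan gives no figure for laboratory tests, so the illustration uses its evaluable number of 642 per arm (protocol section 11, SAP section 6). That number reproduces. With pc = 0.5932, RR = 1.07, pt = 0.6347, margin 0.937, one-sided alpha 0.025 and power 85%,

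n = [(1−pt)/pt + (1−pc)/pc] × (1.960+1.036)² / (ln 1.07 − ln 0.937)² = 1.261 × 8.978 / 0.1327² ≈ 642.8,

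which is 643 when rounded up. After the 10% dropout allowance the plan randomises 715 per arm.

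**Significance level.** Two-sided 0.05 for all analyses other than the primary (protocol 12.2).

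**Assumption.** Let d be the mean change in units of the SD of the change, identical in both arms, so that there is no treatment difference. The documents give no laboratory SDs or expected changes, so a range is shown.

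**If the paired test is run by arm.** The chance that it rejects in one arm is approximately

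p = Φ(d√n − 1.96) + Φ(−d√n − 1.96).

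For d = 0.10 and n = 642, d√n = 2.53, so p ≈ Φ(0.57) ≈ 0.72. The chance that exactly one arm is significant is 2p(1−p). Exact values from the noncentral t distribution:

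| d | p, n = 642 | exactly one arm, n = 642 | p, n = 715 |
|---|---|---|---|
| 0 | 0.05 | 0.095 | 0.05 |
| 0.05 | 0.244 | 0.369 | 0.267 |
| 0.10 | 0.716 | 0.407 | 0.761 |
| 0.15 | 0.967 | 0.064 | 0.980 |
| 0.20 | 0.999 | 0.002 | 1.000 |

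**If the paired test is pooled over arms.** With n = 1284 and d = 0.10, d√n = 3.58 and the rejection probability is about Φ(1.62) ≈ 0.95. The result then carries no information about the arms at all.

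**Between-arm comparison of change.** The shared drift cancels, so the error rate per test stays at 5% for every d (simulated 0.052 at d = 0.20, n = 642). The half-width of the 95% interval is about 1.96 × √(2/642) ≈ 0.11 SD of the change.

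**Which rule governs?** Section 12.5 is the specific text and names only the paired test. The rules in 12.2 and the summary are general. Section 12.2 leaves the specific process to the SAP. SAP section 9 refers the detail back to the protocol, and SAP section 13 is silent on laboratory values. Nothing settles the question.

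**The case against.** The strongest reply is that the plan does contain between-group tests for quantitative data. Section 12.2 prescribes them, and the summary does so under safety endpoints, with confidence intervals. Section 12.5 places laboratory evaluation under its other safety endpoints. The seven listed safety endpoints are all incidences or mortality, so the quantitative clause in the summary arguably has to refer to something beyond them. This has force. A reader might infer from 12.5 that no between-arm laboratory test is planned anywhere, and the documents do not support that. What remains is a conflict: 12.5 calls laboratory data descriptive and gives them a different test, and section 8.3 does not list them as endpoints.

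A reader might also infer that the trial cannot answer its comparative safety question. That is not supported either. All seven items that define the question are compared between arms (protocol 12.5, SAP section 13).

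Nor would every laboratory signal go untested. Abnormal tests count as adverse events (protocol 9.1.1), and the SAP compares adverse events between arms by system organ class and preferred term. The phase 2 contrast in decreased fibrinogen (3/59 on alteplase, none on rhTNK-tPA) is an adverse-event count, so it would be tested if it recurred as recorded events. That route depends on someone judging and recording the abnormality as an event, and it does not see a shift in means that stays below that threshold.

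Two further points stand. The by-arm reading is an inference, and the figures for one arm depend on it. And the plan nowhere says that one-arm significance will be read as a drug effect. That misreading is a risk, not a stated intention.

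**Conclusion.** The point holds in a limited form. The only test that the laboratory-specific text names is uninformative about the treatment difference and does not do what it is said to be for. Its relation to the general between-group rules is unresolved, and the SAP does not resolve it.

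The size depends on an assumed drift. At 642 per arm, with testing by arm, the rejection rate without any arm difference runs from 24% at 0.05 SD to nearly 100% at 0.20 SD. It is about 72% at 0.10 SD, where a split result (one arm significant, the other not) has probability about 0.41. The unsuitability of the test does not depend on these figures.

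Severity is low. These are supportive data, and the main safety comparisons are untouched.

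**What to change.** In protocol 12.5, with matching text in SAP section 13:

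1. Remove the paired t test, and state how laboratory values relate to the rules in 12.2 and the summary.
2. For each quantitative laboratory value with a pre-dose measurement, coagulation included, report the between-arm difference at 24 h and at day 7 or discharge, adjusted for the pre-dose value, with a 95% confidence interval. Label these results supportive and unadjusted for multiplicity.
3. Present shift tables by arm, with a risk difference and 95% confidence interval for moving from normal to clinically significant abnormal.
4. Keep before/after summaries as description, without p-values.

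The cost is wording and a small change to table programs, with no new data, visits or patients. There are two drawbacks. The before/after p-values disappear. And many intervals are reported: section 7.1 lists 26 blood analytes, so two visits give up to 52 intervals. If the drugs did not differ on any of them, about 52 × 0.05 = 2.6 would be expected to exclude zero by chance, which is why the label in item 2 is needed.
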